Biomarkers of inflammation in critically ill children. In a prospective cohort study, PI [name] measured plasma factor VIIIa after insertion of an untunneled CVC in 85 critically ill children.⁴¹ Factor VIIIa was measured at the Clinical Laboratory at Yale-New Haven Hospital with a 1-stage clotting assay (Dade® Actin® FSL, Siemens Healthcare) using the BCS XP System (Siemens Healthcare, Germany). Mean (SD) of factor VIIIa was 133 (61) IU/dL. The incidence of CADVT doubled (95% CI: 1.1-3.6) for every SD increase in factor VIIIa.

PI [name] measured IL-6 and IL-8 in platelet-poor plasma from 10 critically ill adolescents using Milliplex® MAP kits and the Millipore Luminex 200 System (EMD Millipore Corp., Germany) located at the Immune Monitoring Core Facility at Yale. Mean (SD) of IL-6 was 129 (199) pg/mL and 97 (161) pg/mL for IL-8.

Rationale for Trial and Selected Patients

CADVT is a significant problem in critically ill children. It occurs in 18% of children with untunneled CVC and is associated with adverse outcomes.⁵ These outcomes include prolonged stay in the ICU, increased risks of catheter-associated bloodstream infection, pulmonary embolism, and mortality, and increased costs of care.^{1, 2, 6, 7, 9-11} Despite the adverse outcomes associated with CADVT, prophylaxis is not recommended in children because of the absence of data on its efficacy in preventing CADVT in children.⁵ The recommendation to provide prophylaxis in critically ill adults should not be routinely applied to children because of differences in the hemostatic system between these age groups.¹² This trial will explore the efficacy of early prophylaxis against CADVT in critically ill children.

We will enroll children >36 weeks corrected gestational age to <18 years old. This age

range represents the patient population admitted to the pediatric ICU. PROTEKT enrolled children in the same age range.¹⁹ We will only enroll children with untunneled CVC, the most common type used in critically ill children, to minimize confounding based on type of CVC.⁵ Only children with CVC in the internal jugular or femoral veins will be eligible to minimize bias related to the accuracy of ultrasound in diagnosing CADVT.²² We will exclude children at high risk of bleeding such as those with coagulopathy, known bleeding disorder, recent history of clinically relevant bleeding, surgery or trauma, in renal failure, or those on another antithrombotic agent, to minimize the risk of bleeding.

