day 2 with an average exposure ratio of about 15% higher than after a single dose. Steady-state enoxaparin activity levels are well predicted by single-dose pharmacokinetics. After repeated subcutaneous administration of the 1 mg/kg twice daily regimen, the steady state is reached from day 4 with mean exposure about 65% higher than after a single dose and mean peak and trough levels of about 1.2 and 0.52 IU/mL, respectively. Based on enoxaparin sodium pharmacokinetics, this difference in steady state is expected and within the therapeutic range.

Metabolism

Enoxaparin sodium is primarily metabolized in the liver by desulfation and/or depolymerization to lower molecular weight species with much reduced biological potency.⁴⁵ Renal clearance of active fragments represents about 10% of the administered dose and total renal excretion of active and non-active fragments 40% of the dose.

Excretion

Following intravenous dosing, the total body clearance of enoxaparin is 26 mL/min.⁴⁵ After intravenous dosing of enoxaparin labeled with the gamma-emitter, 99mTc, 40% of radioactivity and 8 to 20% of anti-Xa activity were recovered in urine in 24 hours. Elimination half-life based on anti-Xa activity was 4.5 hours after a single subcutaneous dose to about 7 hours after repeated dosing. Following a 40 mg subcutaneously once a day dose, significant anti-Xa activity persists in plasma for about 12 hours. Following subcutaneous dosing, the apparent clearance of enoxaparin is approximately 15 mL/min

Drug Interactions

Unless really needed, agents which may enhance the risk of hemorrhage should be discontinued prior to initiation of Lovenox Injection therapy. These agents include medications such as: anticoagulants, platelet inhibitors including acetylsalicylic acid, salicylates. If co-administration is essential, conduct close clinical and laboratory monitoring.

Drug Supply

Specific manufacturer/supplier of Enoxaparin Sodium Injection, USP is up to the discretion of the participating site as long as the product's FDA application has NDA 020164 as the RLD.

Drug Dose

For prophylaxis, enoxaparin is started at 0.75 mg/kg subcutaneously every 12 hours for children \leq 2 months old or 0.5 mg/kg (maximum dose of 30 mg) subcutaneously every

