12 hours for children >2 months old.^{12, 23} The dose is adjusted to a target anti-Xa activity of 0.2-0.5 IU/mL.^{23, 46, 47} In the absence of prior trials in children, the same target anti-Xa activity recommended in adults will be used in this trial.²³ Among post-operative orthopedic patients on prophylactic dose of LMWH, the mean peak anti-Xa activity on Days 1, 3, 4 and 10 were 0.29, 0.25, 0.33 and 0.37 IU/mL. In acutely ill medical patients, the prophylactic dose of LMWH achieved anti-Xa activity of 0.21 to 0.41 IU/mL. Dose calculations are completed per local standards. An example dose calculation work sheet is provided in Appendix 2.

Rationale for Dose Selection/Regimen

The selection of doses to be used in this trial is based on commonly used doses for the drug.¹⁷ When prescribing enoxaparin in children as prophylaxis against DVT, the starting dose is typically 0.75 mg/kg for children ≤2 months old or 0.5 mg/kg (maximum of 30 mg) for older children. The present trial will utilize this dose as a starting point because of the proven tolerability in clinical care. The maximum dose is based on FDA-approved doses in adults. At these doses, enoxaparin has been shown to be safe without any significant increase in the risk of clinically relevant bleeding.⁴³

Reconstitution

Dilute Enoxaparin Sodium Injection, USP with sterile water for injection or normal saline. Draw up the appropriate dose in a polypropylene plastic tuberculin syringe sealed with a rubber tip cap.

Storage and Stability Requirements

Enoxaparin should not be stored above 25°C and should not be frozen.⁴⁵ When stored at 20°C to 22°C, enoxaparin, 1.2 mg/ml in normal saline, was stable for up to 48 hours. Enoxaparin when repackaged from commercial 0.3 mg syringes of enoxaparin, 100 mg/mL, into tuberculin syringes retained activity and sterility and remained pyrogen free for up to 10 days at 3°C. Undiluted enoxaparin lost activity within 2 days at 22°C. Enoxaparin diluted with sterile water for injection to 20 mg/ml, and stored at room temperature or under refrigeration, was stable for up to 4 weeks in glass or prefilled syringes, as measured by anti-Xa activity.

Handling

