The sponsor (or designee) will review with the investigator and relevant site personnel the procedures for documenting receipt of IP, as well as the procedures for counting, reconciling IP, and documenting this process. Used (and/or empty) syringes of enoxaparin will be destroyed locally. Unused syringes will be destroyed locally after sponsor's approval for destruction. Documentation of all used and unused drug disposal must be maintained on site for review during monitoring visits.

Contraindications

Enoxaparin is contraindicated in patients with active major bleeding, in patients with thrombocytopenia associated with a positive in vitro test for anti-platelet antibody in the

presence of enoxaparin sodium, or in patients with hypersensitivity to enoxaparin sodium. Patients with known hypersensitivity to heparin or pork products should not be treated with enoxaparin or any of its constituents.

Warnings and Precautions

Enoxaparin is not intended for intramuscular administration. Enoxaparin cannot be used interchangeably (unit for unit) with UFH or other LMWH as they differ in manufacturing process, molecular weight distribution, anti-Xa and anti-IIa activities, units, and dosage. Each of these medicines has its own instructions for use. Enoxaparin should be used with extreme caution in patients with a history of HIT. Please refer to package insert for additional information.

Hemorrhage. Enoxaparin, like other anticoagulants, should be used with extreme caution in conditions with increased risk of hemorrhage. Cases of epidural or spinal hematomas have been reported with the associated use of enoxaparin and spinal/epidural anesthesia or spinal puncture resulting in long-term or permanent paralysis.

Major hemorrhages including retroperitoneal and intracranial bleeding have been reported. Some of these cases have been fatal. Bleeding can occur at any site during therapy with enoxaparin. An unexplained fall in hematocrit or blood pressure should lead to a search for a bleeding site.

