Subjects will be identified through regular clinical care in the pediatric ICU by the participating investigators and research staff. All children who had a CVC inserted within the prior 24 hours will be included in a screening log maintained in the pediatric ICU at each site. The screening log will be used to identify potential study participants to be screened for eligibility, record the number of eligible, and ineligible children and reason for exclusion. Eligible children who were not enrolled will also be captured in this log and the reason they were not enrolled (parental refusal, time, etc.). It will also track those children who were eligible and consented but not treated. Treatment with enoxaparin needs to be started within 24 hours after insertion of the CVC, therefore children can be screened for study if CVC insertion occurred within 24 hours of admission to the pediatric ICU or during their stay in the ICU. If a child meets all eligibility criteria, parental permission/assent will be obtained.

Inclusion Criteria

1. Untunneled CVC inserted in the internal jugular or femoral vein within the past 24 hours
2. Child anticipated to stay in the pediatric ICU ≥ 48 hours
3. CVC anticipated to be required for ≥ 24 hours
4. >36 weeks corrected gestational age to <18 years old

Exclusion Criteria

1. Coagulopathy (i.e., international normalized ratio >2.0, activated partial thromboplastin time >50 seconds or platelet count <50,000/mm³)
2. Known bleeding disorder
3. Clinically relevant bleeding as defined by the International Society on Thrombosis and Hemostasis (i.e., Hb decreased ≥ 2 g/dl in 24 hours, required medical or surgical intervention to restore hemostasis, or in a critical organ system [i.e., retroperitoneum, pulmonary, intracranial or central nervous system])
4. <60 days from a clinically relevant bleeding as defined above
5. <7 days after trauma or surgery
6. Anticipated surgery within 48 hours after insertion of the CVC
7. Renal failure (i.e., creatinine clearance <30 mL/min)

8. Presence of epidural catheter
9. Currently taking an antithrombotic agent (e.g., LMWH, UFH at therapeutic doses, Coumadin and aspirin)
10. Radiologically documented DVT at the site of insertion of the CVC in the previous 6 weeks
11. Known hypersensitivity to heparin or its components, including pork products
12. History of HIT (i.e., positive serotonin release assay)
13. Currently pregnant
14. Currently lactating
15. Prior enrollment in the study

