The dose of enoxaparin will be adjusted to a target anti-Xa activity of 0.2-0.5 IU/mL.^{23, 46, 47} The target anti-Xa activity is a peak level and, therefore, timing is extremely important. The peak level must be drawn 4-6 hours after the dose is actually administered. If the child has other labs ordered which are not time dependent, the other labs should be drawn at the same time the enoxaparin peak level is needed.

Using standard methods, anti-Xa activity will be measured 4-6 hours after a dose at the following time points:

1. After the first 3 doses. If needed, the dose will be adjusted to achieve the target anti-Xa activity. See Table 2 for dose titration.
2. After the 3rd dose of a dose titration until the target anti-Xa activity is reached. Once the anti-Xa activity is within target, the dose will be maintained. See Table 2 for dose titration.
3. Weekly to ensure adequate dosing. Similar dose titration as listed in Table 2 will be done to achieve adequate dosing.

Table 2: Enoxaparin Dosage Titration

Anti-Xa Activity	Enoxaparin Dose Titration	Next Anti-Xa Activity Check
<0.10 IU/mL	Increase dose by 20%	After 3 rd dose.
0.10-0.19 IU/mL	Increase dose by 10%	After 3 rd dose.
0.20-0.50 IU/mL	Keep same dosage	Weekly
0.51-1.00 IU/mL	Decrease dose by 10%	After 3 rd dose.
>1.00 IU/mL	Hold all doses until anti-Xa is 0.3, IU/mL, then decrease dose by 20%	Before next dose and every 12 hours, until anti-Xa <0.3 IU/mL

(Modified from Monagle P, et al. *Chest*, 2001, 119:344S)⁵⁰

Discontinuing enoxaparin

The child will be removed from the study and Enoxaparin will be discontinued for the purposes of the study if ANY the following occur:

1. A clinically relevant bleeding event
 - a. Drop in Hb of ≥ 2 g/dl in 24 hours
 - b. Blood product transfused for the bleeding event
 - c. Required medical or surgical intervention to restore hemostasis
 - d. In a critical organ (*i.e.*, retroperitoneum, pulmonary, intracranial or central nervous system)
2. HIT is diagnosed (*i.e.*, positive serotonin release assay)

Holding the Dose

Enoxaparin will be stopped temporarily if ANY the following occur

1. Coagulopathy (*i.e.*, international normalized ratio >2.0, activated partial thromboplastin time >50 seconds or platelet count <50,000/mm³) develops

2. 12 hours before surgery or invasive procedure
3. In cases of suspected HIT (*i.e.*, an unexplained decrease in platelet count $<50,000/\text{mm}^3$ or by 50% of baseline value in the ICU).

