site investigators within 15 calendar days.

A safety monitor is responsible for ongoing timely monitoring of reports of all SAEs submitted by site PIs, or other sources to ensure high-quality reporting, good clinical care and to quickly identify safety concerns. The identification of SAEs will begin when a member of the local research team reports an adverse event. The local research team will monitor each child daily for pre-defined adverse events, particularly clinically relevant bleeding. The research team will interview the clinical team and review the medical records daily for these events. The site PI or his/her designee will conduct prompt investigations of all reported adverse events, especially bleeding. All SAEs will be documented on a SAE form, entered in OnCore and communicated to the PM as soon as possible and <24 hours of the site PI knowing the event.

SAEs will be reported to the Yale Human Investigation Committee and the IRBs of the participating sites per policy.

Adverse Event Committee (AEC)

PI [name] will assemble an independent 3-member AEC composed of a pediatric hematologist (chair), a pediatric intensivist and a nurse. The responsibility of the AEC is to classify all AEs for publication and presentation purposes.

Minimizing Risks

To minimize the risk of bleeding, we will exclude children at high risk of bleeding. Enoxaparin will be held immediately and permanently after a clinically relevant bleeding event as defined by the International Society on Thrombosis and Hemostasis.⁵² Bleeding from enoxaparin can be reversed with protamine or administration of fresh frozen plasma. See section on Holding the Dose, which contains criteria for holding enoxaparin temporarily and when to restart the drug. Enoxaparin will not be replaced with another agent while the drug is on hold.

Platelet count will be monitored for the development of HIT. Enoxaparin and all heparin-related products will be held temporarily for unexplained decrease in platelet count.^{14, 53} Enoxaparin will not be restarted until the child tests negative for HIT.

Subcutaneous administration of enoxaparin may cause pain. As per local ICU practice, enoxaparin may be given through a subcutaneous catheter.

It is unlikely that the blood draws will result in anemia. Packed red blood cells can be transfused for anemia per the direction of the clinical team.

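### Two entry exclusions for bleeding risk, creatinine clearance below 30 mL/min and an epidural catheter in place, have no matching rule in the on-treatment hold and restart criteria

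*Combined protocol and SAP*

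**What the plan says.** Exclusion Criteria item 7 is "Renal failure (i.e., creatinine clearance <30 mL/min" and item 8 is "Presence of epidural catheter". The Rationale for Trial and Selected Patients gives the reason for the renal exclusion, which sits in a list ending "surgery or trauma, in renal failure, or those on another antithrombotic agent, to minimize the risk of bleeding". Warnings and Precautions states that "Cases of epidural or spinal hematomas have been reported with the associated use of enoxaparin and spinal/epidural anesthesia or spinal puncture", with lasting paralysis as a consequence.

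For children already on the drug, Minimizing Risks sends the reader to one place: "See section on Holding the Dose, which contains criteria for holding enoxaparin temporarily and when to restart the drug". That section begins "Enoxaparin will be stopped temporarily if ANY the following occur" and names three triggers: coagulopathy, an operation or invasive procedure (held from 12 hours ahead), and suspected HIT. Restarting the Dose allows treatment to resume a day after coagulopathy has been corrected, a day after the procedure, or once HIT is excluded. The permanent stop reasons, in Discontinuing Enoxaparin and Duration of Therapy, contain no renal or epidural item.

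Safety Laboratory Procedures schedules creatinine within 48 hours of enrollment and at least weekly after that.

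**The concern.** The protocol treats both states as unsafe for starting enoxaparin but does not say what to do when either arises during treatment. The renal signal is already being collected, so what is missing is an action threshold. The text that follows the hold list puts management of the enoxaparin dose in the study's hands and leaves general clinical care with the treating physician. A site would therefore look to the protocol for the rule and not find one. At stake is avoidable bleeding risk, including epidural hematoma, in critically ill children in the enoxaparin arm.

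**Working it through.** The plan states no figure here, so the check sets each bleeding-related entry exclusion beside its on-treatment rule.

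| Entry exclusion | On-treatment rule |
|---|---|
| Coagulopathy (INR >2.0, aPTT >50 s, platelets <50,000/mm³) | Temporary hold at the same thresholds; restart 24 h after correction |
| Clinically relevant bleeding | Permanent stop |
| HIT | Hold on suspicion, stop on diagnosis |
| Recent or planned surgery | Hold from 12 h before; restart 24 h after |
| Other antithrombotic agents | Not allowed; starting therapeutic anticoagulation ends treatment |
| Creatinine clearance <30 mL/min | None, although creatinine is scheduled |
| Epidural catheter in place | None specific to the catheter |

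**Renal.** The section Treatment Regimen with Enoxaparin halves only the initial dose, and does so below 75 mL/min/1.73 m². Take two illustrative children. One enters at 60 and starts on half the dose. The other enters with normal function and falls to 25 on treatment; the body text gives that child neither a reduction nor a stop. Two partial safeguards remain.

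- *Anti-Xa titration (Table 2).* Drug is withheld only above 1.00 IU/mL, which is 1.00 / 0.50 = 2.0 times the upper end of the target range. From 0.51 to 1.00 dosing continues with a 10% cut. Once the level is in target it is checked weekly.
- *Appendix II worksheet.* It asks for GFR again and halves the dose below 75, with no stop at 30. Its status is also limited, since Drug Dose says: "Dose calculations are completed per local standards. An example dose calculation work sheet is provided in Appendix 2".

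**Epidural.** Insertion can reasonably be read as an invasive procedure, so the drug would be off from 12 hours beforehand. The restart clock then runs from the procedure and carries no condition that the catheter be out. From 24 hours after insertion, the restart rule is met while the child is in a state that would have barred entry. Treating removal as a second procedure would add another hold around removal but leave the interval between the two uncovered.

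**Size.** With 1:1 randomization of 100 children, about 50 are exposed. The documents do not say how often renal failure develops or an epidural catheter is placed during treatment, so this number cannot be turned into expected events.

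**The case against.** The best case against the renal point is that clearance at entry is a proxy for exposure, needed because no anti-Xa level exists before the first dose. On treatment, drug activity is measured directly and the dose follows it. The Metabolism section adds that "Renal clearance of active fragments represents about 10% of the administered dose". This stands as a reason not to claim that the drug accumulates or that bleeding rises by any stated amount. It does not explain why 30 mL/min is disqualifying on day 0 and carries no instruction afterwards.

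On the epidural point, the population makes placement uncommon: recent surgery or trauma, and surgery expected within 48 hours of line insertion, are exclusions. Warnings and Precautions also urges extreme caution where hemorrhage risk is raised. Both are fair. But treatment can run to 28 days, and a general caution is not a dosing rule.

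Three stronger readings are tempting and are not supported.

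- A reader might infer that the protocol permits dosing with an epidural catheter in place. No sentence says so; the protocol is silent.
- A reader might infer that the INR and aPTT triggers cannot work because neither test is in the safety labs or the Trial Flow Chart. The hold acts on any clinical result, and restart after correction already implies a repeat test. Routine scheduled testing would add blood volume for little yield.
- A reader might want the dose halved again whenever GFR falls below 75 on treatment. That could halve a dose already titrated to target. If levels then stayed below 0.10 IU/mL, recovery would take four 20% steps (1.2⁴ = 2.07), each after three 12-hourly doses: 4 × 36 h = 144 h, or 6 days. At 0.10–0.19 IU/mL it would take eight 10% steps (1.1⁸ = 2.14): 8 × 36 h = 288 h, or 12 days. Mean catheterization in the investigators' earlier cohorts was 6 days.

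**Conclusion.** The point holds as an omission in the safety rules and should be fixed. The renal part is firm: an entry limit set to reduce bleeding, a scheduled measurement, and no action attached to it. The epidural part rests on silence, read against the protocol's own exclusion and warning. The treating physician may act sooner in either case, but daily bleeding assessment and notification of the DSMB chair at five clinically relevant bleeds respond only after bleeding has occurred.

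The documents support no estimate of excess bleeding. Sample size, the Bayesian decision rules and the primary analysis are unaffected. The conclusion assumes that sites follow the body text and treat the worksheet as the example it is said to be.

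**What to change.** Add two lines to Holding the Dose, with matching lines in Restarting the Dose:

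1. Creatinine clearance below 30 mL/min on any scheduled or clinically ordered result. Restart only when it is back to at least 30 mL/min. Name the estimate to be used, because the exclusion is in mL/min while the dose-halving rule uses the Schwartz value per 1.73 m².
2. An indwelling epidural catheter. Restart no sooner than 24 hours after its removal.

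Also make explicit what the coagulopathy restart rule implies: after a hold triggered by INR or aPTT, restart requires a repeat result that has normalised, meaning INR no higher than 2.0 or aPTT no longer than 50 seconds.

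The cost is a short amendment and some held doses. No new scheduled test is needed, since the renal line uses creatinine already collected. Held doses should be recorded apart from missed doses, because the proportion of missed doses is a compliance outcome. A temporary hold is not among the triggers for an early study ultrasound, so the timing of the primary outcome does not change.

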Thrombocytopenia. Thrombocytopenia can occur with the administration of enoxaparin in adults. Moderate thrombocytopenia (platelet counts between 100,000/mm³ and 50,000/mm³) occurred at a rate of 1.3% in patients given enoxaparin, 1.2% in adults given UFH, and 0.7% in adults given placebo in clinical trials.⁴⁵ Platelet counts less than 50,000/mm³ occurred at a rate of 0.1% in adults given enoxaparin, in 0.2% of adults given UFH, and 0.4% of adults given placebo in the same trials. Thrombocytopenia of any degree should be monitored closely. Cases of HIT with thrombosis have also been observed in clinical practice.

Elevations of serum aminotransferases. Asymptomatic increase in aspartate and alanine aminotransferase levels greater than 3x the upper limit of normal of the laboratory reference range have been reported in up to 6.1% and 5.9% of patients, respectively, during treatment with enoxaparin.

Adverse Reactions

Hemorrhage. The incidence of major hemorrhagic complications with enoxaparin treatment has been low.

Local Reactions. Mild local irritation, pain, hematoma, ecchymosis, and erythema may follow subcutaneous injection of enoxaparin.

Other Reactions. Diarrhea and nausea have also been reported with enoxaparin treatment.

STUDY PLAN AND PROCEDURES

Study Population

We will enroll 100 critically ill children between the ages >36 weeks corrected gestation age and <18 years admitted to the pediatric ICUs of the six participating sites and with a CVC.

Screening Procedures

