Another agent will not be used while enoxaparin is held. Activities related to the management of the dose of enoxaparin will be the purview of the study. However, the clinical care of the child remains with the treating physician.

Restarting the Dose

Timing for restarting treatment

1. 24 hours after coagulopathy is corrected
2. 24 hours after surgery or procedure
3. After exclusion of HIT (*i.e.*, negative serotonin release assay)

Safety Laboratory Procedures and Assessments

Complete blood count, renal function tests (BUN and creatinine), and serum aminotransferases will be done within 48 hours of enrollment and at least weekly ± 2 days, thereafter. An unexplained decrease in platelet count $<50,000/\text{mm}^3$ or by 50% of baseline value in the ICU will trigger a work up for HIT (*i.e.*, send blood for serotonin release assay). Stool occult bleed will be done if clinically indicated as determined by the local investigator.

Bleeding Assessment

Bleeding assessments will be completed by the site study team on a daily basis. The team will interview the clinical care team and review the medical records for the presence of a bleed. The Bleeding Assessment Tool (Appendix III) will be completed for each episode of bleeding. This tool contains questions regarding the site, severity and timing of bleeding.

Concomitant Medications

Antithrombotic agents, including other LMWH, UFH at therapeutic doses, Coumadin and aspirin, are not allowed during the trial.

Diet and Other Considerations

There are no dietary or food restrictions with enoxaparin

Rescue Medication and Supportive Case

In case of a clinically relevant bleed, the clinical team will decide whether blood products should be administered. Protamine may also be used to control the bleeding. For suspected HIT, serotonin release assay will be done. Aside from stopping all

heparin or heparin-related products, no other therapies are needed for HIT.

Duration of Therapy

Enoxaparin will be administered every 12±2 hours until CVC removal, or earlier if the following occur:

1. Discharge from the ICU
2. Radiologic diagnosis of CADVT
3. Start of therapeutic anticoagulation
4. Clinically relevant bleed develops
5. HIT is diagnosed
6. 28 days after insertion of the CVC

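### The protocol gives differing directions for suspected HIT, and it both removes a child with confirmed HIT from the study and keeps that child on study until the ultrasound

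*Combined protocol and SAP*

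**What the plan says.** The protocol treats suspected and confirmed HIT separately.

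- **Suspected HIT.** Under Holding the Dose, "Enoxaparin will be stopped temporarily if ANY the following occur", and the third item on that list begins "In cases of suspected HIT". The paragraph that closes the list states: "Another agent will not be used while enoxaparin is held". It then gives management of the enoxaparin dose to the study, but adds that "the clinical care of the child remains with the treating physician". Minimizing Risks repeats the bar in other words: "Enoxaparin will not be replaced with another agent while the drug is on hold".
- **Confirmed HIT** (positive serotonin release assay). Under Discontinuing enoxaparin, the lead sentence is "The child will be removed from the study and Enoxaparin will be discontinued for the purposes of the study if ANY the following occur", and diagnosed HIT is the second item.
- **Either.** Rescue Medication and Supportive Case orders the assay for suspected HIT and then says that, apart from stopping all "heparin or heparin-related products, no other therapies are needed for HIT".

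Four other places bear on this. Concomitant Medications disallows antithrombotic agents for the duration of the trial. Treatment Regimen, Duration of Therapy and Ultrasound list the start of therapeutic anticoagulation as an event that ends study treatment and triggers the scan. The end of Duration of Therapy keeps a child on study until 30 hours after the last dose or the study ultrasound, whichever is later. The thrombocytopenia warning in the drug background notes: "Cases of HIT with thrombosis have also been observed in clinical practice".

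**The concern.** HIT is an expected adverse event in this trial and can be serious for the child who has it. The same rescue paragraph leaves the choice of blood products for a bleed to the clinical team, but for HIT it delegates nothing and states a conclusion. A site could take that contrast as intended. Another site could rely on the treating-physician sentence. The protocol does not say which prevails.

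The trial has six sites, so the same event could be managed and recorded in different ways. Confirmed HIT, other thromboembolic events and mortality are secondary outcomes. For suspected HIT, starting therapeutic anticoagulation would also end study treatment and bring the ultrasound forward. For confirmed HIT, the question is whether a child who has been removed from the study still has the scan that supplies the primary outcome.

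**Working it through.** No arithmetic applies to the main point, and the plan has no figure to reproduce. The check sets the sections side by side for the two situations.

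| Section | Direction | Suspected HIT (hold) | Confirmed HIT (discontinuation) |
|---|---|---|---|
| Holding the Dose, closing paragraph | No other agent during a hold | Applies | Does not apply |
| Minimizing Risks | Enoxaparin not replaced during a hold | Applies, but narrower | Does not apply |
| Rescue Medication and Supportive Case | Nothing needed beyond stopping heparin products | Applies as worded | Applies |
| Concomitant Medications | Antithrombotic agents disallowed throughout the trial | Applies | Unclear; depends on when the child leaves the study |
| Holding the Dose, closing paragraph | Clinical care stays with the treating physician | Applies | Applies as a general statement |
| Treatment Regimen, Duration of Therapy, Ultrasound | Start of therapeutic anticoagulation ends treatment and triggers the scan | Applies | Adds nothing; the diagnosis already does both |
| Discontinuing enoxaparin | Removal from the study | Does not apply | Applies |
| Duration of Therapy, last paragraph | On study until the later of 30 hours after the last dose and the ultrasound | Not yet reached | Applies |

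**Suspected HIT.**
1. Under Holding the Dose, the bar covers any use of another agent. Under Minimizing Risks, it covers replacement only. These differ in scope.
2. The broader bar and the treating-physician sentence stand two sentences apart, with no order of precedence.
3. The lists of end-of-treatment events assume that therapeutic anticoagulation may start, while Concomitant Medications disallows antithrombotic agents without exception.
4. A site that reads the broad wording and a site that reads the narrow wording can therefore act differently and both cite the protocol.

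**Confirmed HIT.**
1. The hold wording drops out, because this is a discontinuation.
2. The rescue sentence stays, with no qualification for a child who also has a thrombosis. The drug background records that combination as having been seen.
3. Discontinuing enoxaparin takes the child off the study at diagnosis. Duration of Therapy keeps the child on study until at least the ultrasound, and the Ultrasound section orders that scan when HIT is diagnosed. Both cannot describe the same child between diagnosis and scan.
4. Whether the trial-wide bar on antithrombotic agents still applies in that interval depends on which statement governs.
5. Outcome Measures defines the primary outcome by ultrasound within 24 hours after the end of the study period. If removal is taken literally, that scan could be lost. The Aim 1 text in Statistical Considerations does not say how such a child is analysed.

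**The case against.** The strongest reply is that the statements can be followed together. Saying that no other therapy is needed does not forbid one. A site can stop heparin products, not substitute another prophylactic agent, and leave the rest to the treating physician. If that physician starts therapeutic anticoagulation, the protocol already lists it as an end-of-treatment event. Minimizing Risks already speaks of replacement. The background warning gives no direction on management, so it does not contradict the rescue sentence.

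Much of this stands, and it rules out several stronger readings that a reader might infer:

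- **That the bar on another agent governs a confirmed case.** It does not. Both statements of the bar are tied to a hold, and confirmed HIT is a discontinuation.
- **That the protocol prohibits treatment of HIT.** It does not say so. The rescue sentence is about need.
- **That the background warning shows stopping heparin to be insufficient.** The documents do not say that, and the inference would need outside knowledge.
- **That anticoagulation in a confirmed case brings the scan forward.** The diagnosis has already triggered it.
- **That HIT can arise only in the enoxaparin arm.** Unfractionated heparin is named as barred only at therapeutic doses, so lower-dose exposure is not expressly excluded in either arm.

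The reply does not remove the difference in scope between the two versions of the bar during a hold. Nor does it answer the conflict between removal from the study and remaining on it.

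**Conclusion.** The point holds as an inconsistency of wording in a safety direction. For suspected HIT, the literal text and the treating-physician sentence point different ways. For confirmed HIT, the clearer conflict is between removal from the study and staying on study until the scan. The unqualified rescue sentence and the bar in Concomitant Medications add uncertainty.

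The size cannot be computed, because the documents give no HIT rate. A reader might be tempted to use the adult platelet figures in the thrombocytopenia warning. With 1:1 randomization of 100 children, about 50 receive enoxaparin:

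- Counts below 50,000/mm³: 50 × 0.1% = 0.05 children at the enoxaparin rate, and 50 × 0.4% = 0.2 at the placebo rate.
- Counts of 50,000 to 100,000/mm³: 50 × 1.3% = 0.65 at the enoxaparin rate, and 50 × 0.7% = 0.35 at the placebo rate.

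These are rates of low platelet counts in adults, not of HIT. The lowest category was more common on placebo. A count in the higher band does not by itself meet the protocol's trigger, which is an unexplained fall below 50,000/mm³ or by 50% from baseline. The figures do not measure the problem. That few children will be affected is a judgement, and holds for suspected HIT may be more frequent in critically ill children than these adult rates suggest (an assumption).

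No sample size, prior, decision threshold or other statistical figure changes. The case for acting rests on the seriousness for each child and the low cost of the correction.

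**What to change.** The sponsor's clinicians should reconcile the thrombocytopenia warning, Discontinuing enoxaparin, Holding the Dose, Concomitant Medications, Rescue Medication and Supportive Case, Duration of Therapy, and Minimizing Risks. The amended text should:

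1. Leave one direction for suspected HIT and one for confirmed HIT. Which direction prevails is for the sponsor; none is proposed here.
2. State whether the bar on another agent means replacement of study prophylaxis only, as Minimizing Risks reads, or any agent.
3. Record any agent started, with its date, under the existing event for the start of therapeutic anticoagulation.
4. State when a child with diagnosed HIT leaves the study, and that the ultrasound and outcome data are kept. The same lead sentence also removes children with clinically relevant bleeding, so the clarification can cover both.

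The cost is a text amendment to a few sections with the usual ethics approvals. It needs no extra patients, procedures or analyses.
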